#### **Anti-nuclear antibodya**

#### **Alkaline Phosphatase Isoenzymesa**

#### **Anti-smooth muscle antibody (or anti-actin antibody)a**

---

Abbreviation: Ig = immunoglobulin.

a Assayed by Lilly-designated or local laboratory.

b Reflex/confirmation dependent on regulatory requirements and/or testing availability.

---

## Appendix 5. Blood Sampling Summary

---

This table summarizes the approximate number of venipunctures and blood volumes for all blood sampling (screening, safety laboratories, and bioanalytical assays) during the study. The table below is representative of the cohort for which the highest volume of blood will be drawn.

**Protocol H8H-JE-LAIE Sampling Summary**

Purpose	Blood Volume per Sample (mL)	Number of Blood Samples	Total Volume (mL)
Screening tests a	19.5	1	19.5
Clinical laboratory tests a	12.5	4	50
Pregnancy tests	3.5	2	7
Pharmacokinetics b	2	45	90
Pharmacogenetics	10	1	10
Total			176.5
Total for clinical purposes			180

a Additional samples may be drawn if needed for safety purposes.

b A maximum of 3 samples may be collected at additional time points during the study if warranted.

Leo Document ID = 4fc1c794-6709-49d9-92b2-6cedf961e9e6

Approver: PPD

Approval Date & Time: 16-Apr-2018 15:11:01 GMT

Signature meaning: Approved

Approver: PPD

Approval Date & Time: 16-Apr-2018 15:11:01 GMT

Signature meaning: Approved

2. ABBREVIATIONS

Abbreviations pertain to the Statistical Analysis Plan (SAP) only (not the tables, figures and listings [TFLs]).

AE	Adverse event
ALP	Alkaline phosphatase
ALT	Alanine aminotransferase
AUC	Area under the concentration versus time curve
AUC(0-t _{last})	Area under the concentration versus time curve from time zero to time t, where t is the last time point with a measurable concentration
AUC(0-∞)	Area under the concentration versus time curve from time zero to infinity
%AUC(t _{last} -∞)	Percentage of AUC(0-∞) extrapolated
BQL	Below the lower limit of quantitation
C _{max}	Maximum observed drug concentration
CI	Confidence interval
CL/F	Apparent total body clearance of drug calculated after extra-vascular administration
CRF	Case Report Form
CSR	Clinical Study Report
C-SSRS	Columbia Suicide Severity Rating Scale
CRU	Clinical Research Unit
CV	Coefficient of variation
EC	Early Clinical
ECG	Electrocardiogram
e.g.	For example (Latin: exempli gratia)
ICH	International Council on Harmonisation
LLOQ	Lower limit of quantification
MedDRA	Medical Dictionary for Regulatory Activities
MR	Metabolic ratio
MRE	Magnetic resonance elastography
PK	Pharmacokinetic
QTcF	QT interval corrected using Fridericia's formula

SAP	Statistical Analysis Plan
SD	Standard deviation
TBL	Total bilirubin
TFLs	Tables, Figures, and Listings
$t_{1/2}$	Half-life associated with the terminal rate constant (λ_z) in non-compartmental analysis
t_{max}	Time of maximum observed drug concentration
ULN	Upper limit of normal
V_{ss}/F	Apparent volume of distribution at steady state after extra-vascular administration
V_z/F	Apparent volume of distribution during the terminal phase after extra-vascular administration
WHO	World Health Organization
$\Delta QTcF$	changes from baseline in QTcF

3. INTRODUCTION

This SAP has been developed after review of the Clinical Study Protocol (final version dated 16 April 2018).

This SAP describes the planned analysis of the safety, tolerability, and pharmacokinetic (PK) data from this study. A detailed description of the planned TFLs to be presented in the clinical study report (CSR) is provided in the accompanying TFL shell document.

The intent of this document is to provide guidance for the statistical and PK analyses of data. In general, the analyses are based on information from the protocol, unless they have been modified by agreement between Eli Lilly and Company and Covance Early Clinical (EC) Biometrics. A limited amount of information concerning this study (e.g., objectives, study design) is given to help the reader's interpretation. This SAP must be signed off prior to first subject administration for this study. When the SAP and TFL shells are agreed upon and finalized, they will serve as the template for this study's CSR.

This SAP supersedes the statistical considerations identified in the protocol; where considerations are substantially different, they will be so identified. If additional analyses are required to supplement the planned analyses described in this SAP, they may be performed and will be identified in the CSR. Any substantial deviations from this SAP will be agreed upon between Eli Lilly and Company and Covance EC Biometrics and identified in the CSR. Any minor deviations from the TFLs may not be documented in the CSR.

This SAP is written with consideration of the recommendations outlined in the International Council on Harmonisation (ICH) E9 Guideline entitled Guidance for Industry: Statistical Principles for Clinical Trials¹ and the ICH E3 Guideline entitled Guidance for Industry: Structure and Content of Clinical Study Reports².

4. STUDY OBJECTIVES

4.1 Primary Objective

- To explore the safety and tolerability of single and repeated oral doses of lasmiditan in healthy Japanese subjects, and single oral doses of lasmiditan in healthy Caucasian subjects.

4.2 Secondary Objective

- To evaluate the PK of lasmiditan in healthy Japanese and Caucasian subjects.

4.3 Exploratory Objectives

- To evaluate the PK of metabolites M7, M8, (S,R)-M18, and (S,S)-M18 in healthy Japanese and Caucasian subjects.
- To explore the safety, tolerability, and PK of lasmiditan in female subjects compared to male subjects.

5. STUDY DESIGN

This is a randomized, 3-period, subject- and investigator-blind, crossover study in healthy Japanese and Caucasian subjects.

Subjects will be evaluated for study eligibility ≤ 28 days prior to enrollment. Subjects who fulfil the eligibility criteria will be admitted to the clinical research unit (CRU) on Day -1 in Period 1 (the day before their first dose of lasmiditan or placebo).

Subjects will be enrolled into 1 of 3 cohorts. Within each cohort, subjects will be randomized to a treatment sequence, as indicated in Table 1, Table 2, and Table 3. Randomization will be stratified by sex, such there will be an approximately equal number of male and female subjects in each cohort.

Table 1. Treatment Sequences for Cohort 1; Japanese Subjects

Treatment Sequence	Period 1	Period 2	Period 3
1	Placebo	100 mg lasmiditan	200 mg lasmiditan
2	50 mg lasmiditan	Placebo	200 mg lasmiditan
3	50 mg lasmiditan	100 mg lasmiditan	Placebo

Table 2. Treatment Sequences for Cohort 2; Japanese Subjects

Treatment Sequence	Period 1	Period 2	Period 3 ^a
1	Placebo	400 mg lasmiditan	2 x 200 mg lasmiditan
2	50 mg lasmiditan	Placebo	2 x 200 mg lasmiditan
3	100 mg lasmiditan	400 mg lasmiditan	2 x placebo
4	200 mg lasmiditan	400 mg lasmiditan	2 x 200 mg lasmiditan

^a Doses administered 2 hours apart

Table 3. Treatment Sequences for Cohort 3; Caucasian Subjects

Treatment Sequence	Period 1	Period 2	Period 3
1	Placebo	100 mg lasmiditan	200 mg lasmiditan
2	50 mg lasmiditan	Placebo	200 mg lasmiditan
3	50 mg lasmiditan	100 mg lasmiditan	Placebo
4	50 mg lasmiditan	100 mg lasmiditan	200 mg lasmiditan

After randomization on Day 1, investigational medical product will be administered orally on the morning of Day 1 after an overnight fast of at least 8 hours. Blood samples will be collected for PK analysis predose, and for up to 48 hours postdose in each period. There will be a washout period of approximately 72 hours between dose administrations across periods.

Subjects will be discharged from the CRU following completion of all scheduled procedures on Day 3 of Period 3, as defined in the Schedule of Activities (Section 2 in the protocol), and will attend a follow-up visit 7 to 10 days following discharge from the CRU on Day 3 of Period 3.

Safety and tolerability will be assessed throughout the study by means of an adverse event (AE) review, physical examinations, body weight, vital sign measurements, 12-lead

electrocardiograms (ECGs), clinical laboratory tests, and Columbia-Suicide Severity Rating Scale (C-SSRS).

6. TREATMENTS

The following is a list of the study treatment abbreviations that will be used in the TFLs.

Study Treatment Name	Treatment order in TFL
Placebo	1
2 x Placebo	2
50 mg lasmiditan	3
100 mg lasmiditan	4
200 mg lasmiditan	5
400 mg lasmiditan	6
2 x 200 mg lasmiditan	7

7. SAMPLE SIZE JUSTIFICATION

The sample size is customary for Phase 1 studies evaluating safety and PK, and is not powered on the basis of statistical hypothesis testing.

Subjects who are randomized but not administered treatment may be replaced to ensure that approximately 14 Japanese and 8 Caucasian subjects (approximately 2 per treatment sequence) may complete the study.

8. DEFINITION OF ANALYSIS POPULATIONS

The “Safety” population will consist of all enrolled subjects, whether or not they completed all protocol requirements.

The “Pharmacokinetic” population will consist of all subjects who received at least one dose of study drug and have evaluable PK data. Subjects may be excluded from the PK summary statistics and statistical analysis if a subject has an adverse event of vomiting that occurs at or before 2 times median time of maximum observed drug concentration (t_{max}).

All protocol deviations that occur during the study will be considered for their severity/impact and will be taken into consideration when subjects are assigned to analysis populations.

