**Summary of Study Design:**

This is a randomized, 3-period, subject- and investigator-blind crossover study in healthy Japanese and Caucasian subjects.

Subjects will be enrolled into 1 of 3 cohorts; Japanese subjects will be enrolled into Cohorts 1 and 2, and Caucasian subjects will be enrolled into Cohort 3. Within each cohort, subjects will be randomized to a treatment sequence; there will be 3 treatment sequences in Cohort 1, and 4 treatment sequences in each of Cohorts 2 and 3.

Randomization will be stratified by sex, such that there will be an approximately equal number of male and female subjects in each cohort.

Investigational product will be administered after a fast of at least 8 hours. Blood samples for PK analysis will be collected predose and for up to 48 hours postdose in each period. There will be a washout period of approximately

72-hours between dose administrations across periods. Subjects will attend a follow-up visit 7 to 10 days following discharge from the clinical research unit.

Safety and tolerability will be assessed throughout the study by means of adverse event review, physical examinations, body weight, vital sign measurements, electrocardiograms, clinical laboratory tests, and Columbia-Suicide Severity Rating Scale.

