9. STATISTICAL METHODOLOGY

9.1 General

Data listings will be provided for all data that are databased. Summary statistics and statistical analysis will only be presented for data where detailed in this SAP. For continuous data, summary statistics will include the arithmetic mean, arithmetic standard deviation (SD), median, min, max and N; for log-normal data (e.g. the PK parameters: area under the concentration versus time curve [AUCs] and maximum observed drug concentration [C_{max}]) the geometric mean and geometric coefficient of variation (CV%) will also be presented. For categorical data, frequency count and percentages will be presented. Data listings will be provided for all subjects up to the point of withdrawal, with any subjects excluded from the relevant population highlighted. Summary statistics and statistical analyses will generally only be performed for subjects included in the relevant analysis population. For the calculation of summary statistics and statistical analysis, unrounded data will be used.

Mean change from baseline is the mean of all individual subjects' change from baseline values. Each individual change from baseline will be calculated by subtracting the individual subject's baseline value from the value at the time point. The individual subject's change from baseline values will be used to calculate the mean change from baseline using a SAS procedure such as Proc Univariate.

Data analysis will be performed using SAS[®] Version 9.4 or greater.

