9.3.2 Pharmacokinetic Statistical Methodology

All PK parameters will be summarised by population, as well as population and sex for each treatment, and listed. Plots of mean (+/- SD) plasma concentrations by population, as well as population and sex for each treatment over time will be presented.

Pharmacokinetic parameters for lasmiditan will be evaluated to determine dose proportionality for Japanese (Cohorts 1 and 2 over the 50 to 400 mg dose range, excluding any data from Period 3 in Cohort 2) and Caucasian subjects (Cohort 3, over the 50 to 200 mg dose range). Log-transformed C_{max} and AUC from time 0 extrapolated to infinity [AUC(0- ∞)] will be evaluated using a power model (where the log of the dose will be an explanatory variable and subject will be a random effect) to estimate ratios of dose-normalized geometric means and the corresponding 90% confidence intervals (CIs). The estimated ratio between the highest and lowest doses for each population (Japanese, Caucasian) will be used to assess dose proportionality. The intersubject coefficient of variation (CV) will be derived, and the intrasubject CV will also be derived, as appropriate.

Example SAS code:

```
proc mixed data=pk01;
  by popul param;
  title1 j=c "Estimate of slope";
  class usubjid;
  model log_pk = log_dose / solution residual cl alpha=0.1;
  random usubjid;
  ods output solutionf=doseprop;
run;
```

Additional analysis will be performed if warranted upon review of the data.

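### The SAP's vomiting rule lets a whole subject be dropped from the PK analysis when only one period's profile is affected

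*SAP*

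**What the plan says.** SAP section 8 defines the PK population by subject, as "all subjects who received at least one dose of study drug and have evaluable PK data". It then adds the vomiting rule: "Subjects may be excluded from the PK summary statistics and statistical analysis if a subject has an adverse event of vomiting". The timing condition is part of the same sentence: the rule covers only an event "that occurs at or before 2 times median time of maximum observed drug concentration". The rule names no period, dose or treatment, and no other section narrows it. SAP section 9.1 also works by subject: "Summary statistics and statistical analyses will generally only be performed for subjects included in the relevant analysis population".

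Several features of the design bear on this rule:

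- SAP section 5: "There will be a washout period of approximately 72 hours between dose administrations across periods".
- Protocol section 3.2 gives a terminal half-life of about 4 hours for lasmiditan, and about 4.5 to 21 hours for its metabolites.
- SAP section 9.3.2 summarises PK parameters by population and treatment. It fits the power model to each population separately, "where the log of the dose will be an explanatory variable and subject will be a random effect".
- The SAP does not say whether the median tmax is taken per treatment, per population or over all data. Nor does it say how the window runs when two doses are given 2 hours apart.

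**The concern.** Vomiting soon after a dose can compromise the absorption of that dose. It says nothing against the lasmiditan profiles that the same person gives in other periods. A rule whose unit is the subject therefore allows sound profiles to be discarded together with the doubtful one, in a study with few subjects per dose.

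Two things are at stake. The first is precision, in the dose-proportionality slope and in the geometric means by dose. The second is selection: if the people who vomit tend to have high exposure, removing them altogether also takes them out of the low-dose cells, where nothing went wrong, and would pull those means down.

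**Working it through.** **1. Planned numbers.** The SAP plans that "approximately 14 Japanese and 8 Caucasian subjects (approximately 2 per treatment sequence) may complete the study", and the protocol synopsis says "there will be 3 treatment sequences in Cohort 1, and 4 treatment sequences in each of Cohorts 2 and 3". Japanese: 2 x (3 + 4) = 14. Caucasian: 2 x 4 = 8. Both reproduce the plan.

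**2. Subjects per active dose, from the sequence tables at 2 per sequence.**

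| Population | 50 mg | 100 mg | 200 mg | 400 mg | 2 x 200 mg |
|---|---|---|---|---|---|
| Japanese | 6 | 6 | 6 | 6 | 6 |
| Caucasian | 6 | 6 | 6 | – | – |

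The power model leaves out Cohort 2 Period 3, so it uses 6 x 4 = 24 Japanese and 6 x 3 = 18 Caucasian profiles.

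**3. Washout.** For the parent drug, 72 / 4 = 18 half-lives. For the slowest metabolite, 72 / 21 = 3.4 half-lives.

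**4. Profiles lost when one subject vomits in one active period.** Period-level exclusion loses 1. Subject-level exclusion loses every active profile of that subject:

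- 2 in nine of the eleven sequences, so 1 valid profile goes needlessly;
- 3 in Cohort 2 sequence 4 and Cohort 3 sequence 4, so 2 valid profiles go needlessly.

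Each other dose that the subject received falls from 6 to 5 in that population.

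**5. Effect on the slope.** The documents give no CVs, so between/within-subject CVs of 20/15%, 30/20% and 40/30% are assumed, with log-scale SD = sqrt(ln(1 + CV²)). For subject i, X_i holds a 1 and ln(dose) for each profile, and V_i = σ_b² J + σ_w² I (J is the all-ones matrix). SE(slope) is the square root of the slope element of (Σ X_i' V_i⁻¹ X_i)⁻¹. It was computed for each possible single case, once without the affected profile and once without the subject.

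| Population | Assumed CVs | SE, all data | Extra SE, subject v period exclusion: mean | Maximum |
|---|---|---|---|---|
| Japanese | 20/15% | 0.0530 | 1.1% | 2.8% |
| Japanese | 30/20% | 0.0722 | 1.0% | 2.5% |
| Japanese | 40/30% | 0.1041 | 1.1% | 2.8% |
| Caucasian | 20/15% | 0.0666 | 2.9% | 11.2% |
| Caucasian | 30/20% | 0.0887 | 2.7% | 11.3% |
| Caucasian | 40/30% | 0.1310 | 2.9% | 11.2% |

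The Caucasian maximum is a Cohort 3 sequence 4 subject vomiting at 100 mg. That dose is midway between 50 and 200 mg on the log scale, so losing its profile alone costs the slope nothing (0.0887 at 30/20%). Losing the subject removes a 50 v 200 mg contrast (0.0988). For vomiting at 200 mg in the same sequence the figures are 0.0955 and 0.0988, a difference of 3.4%.

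The table covers vomiting in periods that feed the power model. Vomiting in Cohort 2 Period 3 would remove nothing from that model under period-level exclusion. Under subject-level exclusion it removes the subject's earlier single-dose profiles, and the SE rises by 2.5% to 3.1%.

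**6. On the reported scale.** The Caucasian 200/50 mg dose-normalised ratio has log-scale SE = ln(4) x SE(slope). With a normal quantile of 1.645 and 30/20% CVs, the 90% interval half-width is exp(1.645 x 1.386 x SE). For a sequence 4 subject vomiting at 200 mg it is x/÷1.243 with period exclusion (SE 0.0955) and x/÷1.253 with subject exclusion (SE 0.0988). For vomiting at 100 mg it is x/÷1.224 against x/÷1.253.

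**The case against.** The rule is optional. An analyst could drop only the affected treatment, which the per-treatment summaries would accommodate. Excluded subjects stay in the listings and are highlighted (SAP section 9.1). A reader might infer that the SAP requires valid profiles to be thrown away; it does not. This part stands. Even so, the subject is the only unit of exclusion that the sentence names, and choosing another means departing from its wording.

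The precision loss is also modest. The study is not powered on a hypothesis test, so a change of 1% to 3% in a standard error alters no planned decision. The 11% figure needs one particular sequence and dose. This stands too.

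A reader might go on to infer that the low-dose means will be biased. That depends on vomiting tracking exposure, which the documents do not show. Protocol section 3.2 lists nausea, not vomiting, among the most frequent events. The slope, which rests largely on within-subject contrasts, is better protected than the cell means. Nor is an inferential comparison of populations damaged, because none is planned for PK.

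Finally, period-level exclusion is not free of selection. The affected subject would stay in some dose cells and leave another, so summaries at different doses would cover slightly different people. And the 18 half-lives apply to the parent drug only. Metabolite carry-over at 3.4 half-lives is a weaker guarantee, though it exists whichever exclusion unit is used.

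**Conclusion.** The point holds as a defect in the unit of exclusion. As worded, the SAP permits a whole subject to be removed from the PK summaries and the power model because of an event that compromises one period's dose, although the other parent-drug profiles are valid and both analyses can use them.

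For one case in an active period, the needless loss is one valid profile, or two in the two sequences with three active periods, and the subject's other dose cells go from 6 to 5. The extra slope standard error averages about 3% for Caucasian subjects (maximum about 11%) and about 1% for Japanese subjects (maximum about 3%). These figures rest on two completers per sequence, a single affected subject, and the assumed CVs of 20/15% to 40/30%. Bias in the low-dose cells is possible but conditional. The case for change is that a better rule is available at very little cost; it does not depend on a large loss of precision.

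**What to change.** In SAP section 8, replace the vomiting sentence with wording such as: if vomiting occurs within twice the median tmax after dosing in a treatment period, the PK profile from that period may be excluded from the PK summary statistics and the power model; the subject's profiles from other periods are retained.

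Add two definitions:

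- The median tmax is that of the same treatment.
- For 2 x 200 mg, state how the window is counted. PK sampling times for that regimen run from the first dose, so the SAP must say whether the window starts at the first dose only or at each dose.

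The cost is a few lines of text and no new data. The small downside is that treatment summaries at different doses may then include slightly different subjects. A footnote giving the number of profiles in each cell and the reason for any exclusion deals with that.

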9. STATISTICAL METHODOLOGY

9.1 General

Data listings will be provided for all data that are databased. Summary statistics and statistical analysis will only be presented for data where detailed in this SAP. For continuous data, summary statistics will include the arithmetic mean, arithmetic standard deviation (SD), median, min, max and N; for log-normal data (e.g. the PK parameters: area under the concentration versus time curve [AUCs] and maximum observed drug concentration [C_{max}]) the geometric mean and geometric coefficient of variation (CV%) will also be presented. For categorical data, frequency count and percentages will be presented. Data listings will be provided for all subjects up to the point of withdrawal, with any subjects excluded from the relevant population highlighted. Summary statistics and statistical analyses will generally only be performed for subjects included in the relevant analysis population. For the calculation of summary statistics and statistical analysis, unrounded data will be used.

Mean change from baseline is the mean of all individual subjects' change from baseline values. Each individual change from baseline will be calculated by subtracting the individual subject's baseline value from the value at the time point. The individual subject's change from baseline values will be used to calculate the mean change from baseline using a SAS procedure such as Proc Univariate.

Data analysis will be performed using SAS[®] Version 9.4 or greater.

